## **Technical complaint**

A technical complaint is any written, electronic, or oral communication that alleges product (medicine or device) defects. The technical complaint may be associated with an AE, but does not concern the AE itself.

Examples of technical complaints:

- The physical or chemical appearance of trial products (e.g. discolouration, particles or contamination)
- The packaging material (e.g. leakage, cracks, rubber membrane issues or errors in labelling text)
- Problems related to devices (e.g. to the injection mechanism, dose setting mechanism, push button or interface between the pen and the needle)

## **12.2 Reporting of adverse events**

All events meeting the definition of an AE must be collected and reported. This includes events from the first trial-related activity after the subject has signed the informed consent until the end of the post-treatment follow-up period (Visit 38). The events must be recorded in the applicable eCRF forms in a timely manner, see timelines below and [Figure 12-1](#).

During each contact with the trial site staff, the subject must be asked about AEs and technical complaints, for example by asking: "Have you experienced any problems since the last contact?"

All AEs, either observed by the Investigator or subject, must be reported by the Investigator and evaluated. Novo Nordisk assessment of expectedness is performed according to the following reference documents:

- Faster-acting insulin aspart: Faster-acting insulin aspart IB. Current version and any updates hereof
- NovoRapid®: Company Core Data Sheet. Current version and any updates hereof
- Insulin degludec: Insulin degludec IB. Current version and any updates hereof

All AEs must be recorded by the Investigator on an AE form. The Investigator should report the diagnosis, if available. If no diagnosis is available, the Investigator should record each sign and symptom as individual AEs using separate AE forms.

For SAEs, a safety information form must be completed in addition to the AE form. If several symptoms or diagnoses occur as part of the same clinical picture, one safety information form can be used to describe all the SAEs.

MESIs, regardless of seriousness, must be reported using the AE form, the safety information form and a MESI form. The MESI form is a form tailored to collect specific information related to the individual MESI.

The AE form for a non-serious AE not fulfilling the MESI criteria should be signed when the event is resolved or at the end of the trial.

#### **Timelines for initial reporting of AEs:**

The Investigator must complete the following forms in the eCRF within the specified timelines:

[figure not shown]
- **SAEs:** The AE form **within 24 hours** and the safety information form **within 5 calendar days** of the Investigator's first knowledge of the SAE.

Both forms must be signed within 7 calendar days from the date the information was entered in the eCRF.

- **SAEs fulfilling the MESI criteria:** In addition to above, the MESI form **within 14 calendar days** of the Investigator's first knowledge of the AE.
- **Non-serious AE fulfilling the MESI criteria:** The AE form, safety information form and MESI form **within 14 calendar days** of the Investigator's first knowledge of the event.

If the eCRF is unavailable, the concerned AE information must be reported on paper forms and sent to Novo Nordisk by fax, e-mail or courier within the same timelines as stated above. When the eCRF becomes available again, the Investigator must enter the information on the appropriate forms in the eCRF.

Contact details (fax, telephone, e-mail and address) are provided in the Investigator trial master file.

**Figure 12–1 Initial reporting of AEs**

#### **Reporting of trial product-related SUSARs by Novo Nordisk:**

Novo Nordisk will notify the Investigator of trial product-related suspected unexpected serious adverse reactions (SUSARs) in accordance with local requirements and ICH GCP. In addition, the Investigator will be informed of any trial-related SAEs that may warrant a change in any trial procedure.

In accordance with regulatory requirements, Novo Nordisk will inform the regulatory authorities, including EMA, of trial product-related SUSARs. In addition, Novo Nordisk will inform the institutional review boards (IRBs)/independent ethics committees (IECs) of trial product-related SUSARs in accordance with local requirement and ICH GCP, unless locally this is an obligation of the Investigator.

#### **Novo Nordisk products used as concomitant medication:**

If a SAE and/or MESI is considered to have a causal relationship with a Novo Nordisk marketed product used as concomitant medication in the trial, it is important that the suspected relationship is reported to Novo Nordisk, e.g. in the alternative aetiology section on the safety information form. Novo Nordisk may need to report this adverse event to relevant regulatory authorities.

### **12.3 Follow-up of adverse events**

The Investigator must record follow-up information by updating the forms in the eCRF.

Follow up information must be reported to Novo Nordisk according to the following:

- **SAEs:** All SAEs must be followed until the outcome of the event is “recovered/resolved”, “recovered/resolved with sequelae” or “fatal”, and until all queries have been resolved. Cases of chronic conditions, cancer or AEs ongoing at time of death (where death is due to another AE) may be closed with the outcome “recovering/resolving” or “not recovered/not resolved”. Cases can be closed with the outcome of “recovering/resolving” when the subject has completed the follow-up period and is expected by the Investigator to recover.

The SAE follow-up information should only include new (e.g. corrections or additional) information and must be reported **within 24 hours** of the Investigator's first knowledge of the information. This is also the case for previously non-serious AEs which subsequently become SAEs.

- **Non-serious AEs:** Non-serious AEs must be followed until the outcome of the event is “recovering/resolving”, “recovered/resolved” or “recovered/resolved with sequelae” or until the end of the follow-up period stated in the protocol, whichever comes first, and until all queries related to these AEs have been resolved. Cases of chronic conditions, cancer or AEs ongoing at time of death (where death is due to another AE) may be closed with the outcome “recovering/resolving” or “not recovered/not resolved”. Cases can be closed with the outcome of “recovering/resolving” when the subject has completed the follow-up period and is expected by the Investigator to recover.
- **Non-serious AE fulfilling the MESI criteria:** Non-serious AE fulfilling the MESI criteria must be followed as specified for non-serious AEs. Follow-up information on MESIs should only include new (e.g. corrections or additional) information and must be reported **within 14 calendar days** of the Investigator's first knowledge of the information. This is also the case for previously reported non-serious AEs which subsequently fulfil the MESI criteria.

The Investigator must ensure that the worst case severity and seriousness of an event is kept throughout the trial. A worsening of an unresolved AE must be reported as follow up with re-assessment of severity and/or seriousness of the event.

Queries or follow-up requests from Novo Nordisk must be responded to **within 14 calendar days** from the date of receipt of the request, unless otherwise specified in the follow-up request.

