- **Recovering/resolving** - The condition is improving and the subject is expected to recover from the event. This term is only applicable if the subject has completed the trial or has died from another AE.
- **Recovered/resolved with sequelae** - The subject has recovered from the condition, but with lasting effect due to a disease, injury, treatment or procedure. If a sequela meets an SAE criterion, the AE must be reported as an SAE.
- **Not recovered/not resolved** - The condition of the subject has not improved and the symptoms are unchanged, or the outcome is not known.
- **Fatal** - This term is only applicable if the subject died from a condition related to the reported AE. Outcomes of other reported AEs in a subject before he/she died should be assessed as "recovered/resolved", "recovering/resolving", "recovered/resolved with sequelae" or "not recovered/not resolved". An AE with fatal outcome must be reported as an SAE.
- **Unknown** - This term is only applicable if the subject is lost to follow-up.

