Table 9.2 was updated to reflect the updated in-use storage conditions for insulin degludec and the US approval status of insulin degludec was updated. in section 3.5

Section 12: The period for safety reporting was updated to also accommodate correct collection period for the subjects that discontinue treatment prematurely. The SAE definition section was updated to report potential events of Hy's law using the seriousness criteria 'Important medical event' if no other seriousness criteria apply. It is a regulatory requirement in all clinical trials that events of suspected drug induced liver injury are reported to the regulatory authorities within expedited timelines.

Two new references were introduced in section 5.2.1 (Rationale for choice of non-inferiority margin) and the references to the SmPC for Insulin degludec will be updated to the current version in the updated protocol and the reference to the Investigators Brochure for insulin degludec will be changed to the current version of the Company Core Datasheet in section 12.2.

Appendix A was updated to reflect that it is not the mean pre-prandial blood glucose that is used for titration.

In this protocol amendment:

- Any new text is written *in italics*.
- Any text deleted from the protocol is written using ~~strike-through~~.

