## **2.16 Section 8.1.13 Premature discontinuation of trial product**

*If a subject is prematurely discontinued from trial product after randomisation (Visit 10), the Investigator must ensure every possible effort is made to undertake procedures for Visit 36A, as soon as possible.*

*Treatment discontinuation must be performed in the eDiary web portal. This must be performed at least 4 days prior to Visit 36A to ensure scheduling of the 7-9-7-point profile on the three days prior to Visit 36A.*

*At visit 36A subjects must undergo the meal test before discontinuing trial product. The meal test should be performed with trial drug according to randomisation unless this is not feasible due to safety reasons including pregnancy as judged by the investigator. This must be documented in the eCRF.*

*A "treatment discontinuation" session must be made in the IV/WRS after the meal test has been completed and primary reason for discontinuation of trial product must be specified in the first part of the end-of-treatment/trial form in the eCRF.*

*Final drug accountability must be performed. The subject should be switched to a suitable marketed product at the discretion of the Investigator. The medication should be recorded on the concomitant diabetes medication form in the eCRF, as described in section 8.2.4 at each contact after trial drug discontinuation.*

*The subject should also complete the follow-up visits (visit 37 and phone contact 38). Visit 37 can be converted into a phone contact as collection of the eDiary is not applicable at this visit for the subjects that discontinue trial product prematurely.*

*In addition, subjects prematurely discontinued from trial product should continue with the per protocol planned visits at 4 (Visit 14), 8 (Visit 18), 12 (Visit 22), 16 (Visit 26), 20 (Visit 30), 24 (Visit 34) and 26 (Visit 36) weeks after randomisation depending on when the subject discontinues trial product. The meal test at V36 should be done with the subjects' currently prescribed insulin treatment with a bolus insulin dose of 0.1 U/kg. The eDiary must be returned to the site at the end of visit 36.*

*The following assessments are not applicable for subjects that prematurely discontinue trial product: 4 point profiles, daily doses of trial insulin, time of injection, duration of meal, titration method, dose recommendation, reason for deviation and collection of technical complaints.*

*In the following situations, only one visit should take place:*

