##### **2.29.4.2 Section 17.4.2.2 Safety endpoints**

*All safety endpoints will be compared using the on-treatment observation period. In terms of adverse events, as a minimum, serious adverse events will be tabulated separately also using the in-trial observation period.*

*All events in the in-trial observation period will be listed with information about whether it appeared in the on-treatment observation period or not.*

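### Section 12.3 was not updated with Amendment 2, so required follow-up of non-serious AEs and MESIs in subjects who stop product early ends at phone contact 38, up to months before Visit 36, and its use of 'recovering/resolving' conflicts with 12.1

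*Protocol*

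**What the plan says.** **Follow-up (section 12.3, not amended).** Non-serious AEs are followed until they are recovering, recovered, or recovered with sequelae, "or until the end of the follow-up period stated in the protocol, whichever comes first". Non-serious MESIs follow the same rule. For SAEs the rule is "All SAEs must be followed until the outcome of the event is" recovered, recovered with sequelae, or fatal, with no calendar limit. For both groups, a case may be closed as 'recovering/resolving' "when the subject has completed the follow-up period and is expected by the Investigator to recover". The section also states: "A worsening of an unresolved AE must be reported as follow up with re-assessment of severity and/or seriousness of the event".

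**Outcome terms (section 12.1, Final outcome, not amended).** For 'recovering/resolving': "This term is only applicable if the subject has completed the trial or has died from another AE".

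**Amendment 2.**
- The introduction explains the change to section 12: "The period for safety reporting was updated to also accommodate correct collection period for the subjects that discontinue treatment prematurely".
- Item 2.26 (section 12.2) moves the end of AE collection from Visit 38 to the last phone contact or site visit.
- Item 2.15 (follow-up period) places Visit 37 at 7-12 days and phone contact 38 at 30-35 days after the last day on trial product.
- Item 2.16 (section 8.1.13) has subjects who stop product complete both follow-up contacts and also attend the planned visits to week 26.
- Its list of changes covers 12.1 and 12.2 and then goes to section 14.

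**The concern.** In protocol version 1.0 the limit in 12.3 did no harm. AE collection ended at Visit 38, the follow-up period consisted of Visits 37 and 38, and a withdrawn subject had those contacts and left. The end of follow-up and the last contact were the same moment.

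Amendment 2 separates them for subjects who stop product and stay. Their follow-up contacts come soon after the last dose, while they continue to Visit 36. Section 12.2 was adapted to this and 12.3 was not. Read as written:

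- A non-serious AE still open at phone contact 38, possibly the event that led to stopping, need not be followed further, although the subject keeps attending.
- A non-serious AE that starts after phone contact 38 must be collected, but its follow-up limit has already passed.

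At stake is the final-outcome field for non-serious AEs and MESIs. Amendment 2, section 17.4.2.2, summarises TEAEs by outcome, so an event open at phone contact 38 can enter that summary with an outcome fixed too early.

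**Working it through.** The plan gives no figure for this point, so there is none to reproduce. The check is calendar arithmetic and a comparison of passages.

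**Inputs**
- Phone contact 38: 30-35 days after the last day on trial product (Amendment 2, item 2.15).
- Visit 36: week 26, day 182 (flow chart); the ±3-day window is ignored.
- Treatment discontinuation perhaps as low as 8%, half of it trial discontinuation (Amendment 2, section 17.1).
- Planned randomised: 999 (section 6.1).

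**Length of the gap.** For a stop on day *s*, gap = 182 − (*s* + 30 to 35) days.

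| Stop | Phone contact 38 | Gap to Visit 36 |
|---|---|---|
| Week 4 (day 28) | day 58-63 (week 8.3-9.0) | 119-124 days (17.0-17.7 weeks) |
| Week 12 (day 84) | day 114-119 | 63-68 days (9.0-9.7 weeks) |

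The gap closes when *s* = 182 − 35 = 147 days (week 21.0) or 182 − 30 = 152 days (week 21.7). Later stops are unaffected.

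**Number of subjects.** 0.08 × 999 ≈ 80 stop product; half, about 40, stay in the trial. This is a ceiling at that rate, because late stoppers have no gap.

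**Which events are touched.** A TEAE must start no later than seven days after the last day of treatment. An event that starts after phone contact 38, at day 30-35, is therefore not a TEAE and goes to listings. The summary by outcome is affected only through TEAEs still open at phone contact 38.

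**Sections 12.1 and 12.3 side by side, for 'recovering/resolving'**

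| Situation | 12.3 | 12.1 |
|---|---|---|
| Non-serious AE improving mid-trial | Ends required follow-up | Term not available |
| Any case, SAEs included: follow-up period completed, recovery expected, subject still attending | Case can be closed | Term not available until the trial is completed |

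The first row is already a conflict in version 1.0 and applies to every subject. The second arises for early stoppers because, after Amendment 2, completing the follow-up period and completing the trial are no longer the same event.

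**The case against.** **The follow-up period may lie after week 26 for everyone.** Section 12.3 gives no number of days, and section 5.1 places a 30-day follow-up after the 26-week treatment period. On that reading there is no gap. The term is indeed ambiguous for early stoppers. But Amendment 2 counts the follow-up contacts from the last day on product and gives these subjects no second set after Visit 36. Item 2.17 says that someone who withdraws consent after completing them does not repeat them. The early limit is the more natural reading, and the ambiguity itself needs removing.

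**Sites will keep the forms open anyway.** Under 12.2 the AE form for a non-serious, non-MESI event is signed when the event resolves or at the end of the trial, and subjects are asked about AEs at every contact. This makes late updates possible and likely, but 12.3 does not require them.

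**Two stronger readings are tempting, and neither is supported.**

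- *A reader might infer that worsening after phone contact 38 need not be reported.* Section 12.3 requires worsening of an unresolved AE to be reported as follow-up, without a time limit, and requires the worst severity and seriousness to be kept throughout the trial. An event that becomes serious is reportable within 24 hours.
- *A reader might infer that SAEs can be closed early.* They have no calendar cut-off. The one exception tied to the follow-up period also needs expected recovery, and 12.1 withholds that outcome from a subject who has not completed the trial. The two sections conflict here; together they do not give a licence to close.

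For the same reasons it does not follow that the in-trial SAE tabulation ("serious adverse events will be tabulated separately also using the in-trial observation period") is incomplete: SAEs are collected to the last contact and followed to outcome.

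**Conclusion.** The point holds for non-serious AEs and non-serious MESIs. Section 12.3 was not aligned with amended 12.2 and 8.1.13, so for subjects who stop product before about week 21 and stay in the trial the stated follow-up limit falls before their last contact, by 17.0-17.7 weeks for a stop at week 4. At most about 40 of 999 subjects are concerned at the protocol's 8% rate. The amendment words that rate as a low value, so the number could be higher.

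The consequence is limited to the recorded final outcome of non-serious events, including TEAEs open at phone contact 38. Event counts, SAE outcomes and the reporting of worsening remain covered. The clash over 'recovering/resolving' is a separate inconsistency.

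The conclusion rests on reading the follow-up period as Visit 37 and phone contact 38, counted from the last day on product. It is worth correcting because the rule as written stops follow-up too early in the subjects whom Amendment 2 was designed to retain, and a change of wording removes the problem.

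**What to change.** In section 12.3:

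1. Replace both references to the follow-up period, in the limit for non-serious AEs and in the closure rule for SAEs and non-serious AEs, with the last trial-related contact, defined as the later of Visit 36 and phone contact 38. This matches amended 12.2. For subjects who complete treatment it remains phone contact 38, so nothing changes for them.
2. Reconcile 'recovering/resolving' with 12.1, so that both sections state the same condition for using it and for ending follow-up or closing a case with it.

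The cost is an amendment to the wording of one section, with any matching edit in 12.1, and a few more form updates. The subjects already attend these visits and are already asked about AEs, so no visit or assessment is added.

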## **12.4 Technical complaints and technical complaint samples**

### **12.4.1 Reporting of technical complaints**

All technical complaints on any of the following products:

- Faster-acting insulin aspart, 100 U/mL solution for injection for s.c. injection, 3 mL PDS290 pen injector (blinded)
- Faster-acting insulin aspart, 100 U/mL solution for injection for s.c. injection, 3 mL PDS290 pen injector (open for postmeal arm)
- Insulin aspart, 100 U/mL solution for injection for s.c. injection, 3 mL PDS290 pen injector (blinded)
- Insulin aspart, 100 U/mL solution for injection for s.c. injection, 3 mL PDS290 pen injector (open)
- Insulin degludec, 100U/mL solution for injection for s.c. injection, 3 mL PDS290 pen injector (open)
- Novo Nordisk Needles

which occur from the time of first usage of the product until the time of the last usage of the product, must be collected and reported to Customer Complaint Center, Novo Nordisk.

Contact details (fax, e-mail and address) are provided in [Attachment I](#) to the protocol.

The Investigator must assess whether the technical complaint is related to any AEs, SAEs, and/or MESI.

Technical complaints must be reported on a separate technical complaint form. A technical complaint form for each batch, code or lot number or for each DUN must be completed.

The Investigator must complete the technical complaint form in the eCRF within the following timelines of the trial site obtaining knowledge of the technical complaint:

- Technical complaint assessed as related to an SAE **within 24 hours**
- All other technical complaints **within 5 calendar days**

If the eCRF is unavailable or when reporting a technical complaint that is not subject related, the information must be provided on a paper form by fax, e-mail or courier to Customer Complaint Center, Novo Nordisk, within the same timelines as stated above. When the eCRF becomes available again, the Investigator must enter the information on the technical complaint form in the eCRF.

## **12.4.2 Collection, storage and shipment of technical complaint samples**

The Investigator must collect the technical complaint sample and notify the monitor **within 5 calendar days** of obtaining the sample at trial site. The monitor must coordinate the shipment to Customer Complaint Center, Novo Nordisk (the address is provided in [Attachment I](#)) and ensure that the sample is sent as soon as possible. A print or copy of the technical complaint form must be sent with the sample.

The Investigator must ensure that the technical complaint sample contains the batch, code or lot number and, if available, the DUN.

If the technical complaint sample is unobtainable, the Investigator must specify on the technical complaint form why it is unobtainable.

Storage of the technical complaint sample must be done in accordance with the conditions prescribed for the product. The shipment of the technical complaint sample should be done in accordance with the same conditions as for storage (see section [9](#)).

